9.5.2.1.1 Screening Failure

A screening failure is defined as a patient who has given informed consent and failed to meet at least one inclusion or exclusion criteria as defined by the protocol. Screening failures will not be entered in clinical database.

Eligible patients who meet all inclusion/exclusion criteria but are unable to participate in the study due to different reasons will not be considered screening failures. These patients will not be entered in clinical database.

9.5.2.1.2 Re-screening of Patients

If patients fail screening, re-screening is permitted up to 14 days, if in the opinion of the Investigator the patient may be eligible with a reanalysis of failed variables.

9.5.2.2 Study Examinations

Assessments are to be performed according to the schedule shown in Table 1 and depend on time-point of start of the intervention.

Safety will be evaluated by collecting reported adverse events at regular intervals throughout the study and by the assessment of vital signs, clinical laboratory parameters, ECGs, and adverse events.

9.5.2.2.1 Medical and Medication History

A complete medical and medication history as well as demographic information will be assessed at the time-points indicated in Table 1.

The medical history will be reviewed and recorded, including:

Medical and Medication History

- Recent ingestion of medication (10 days prior to entering the screening period)
- History of respiratory, cardiovascular, renal, gastrointestinal, hepatic, endocrine, haematological, neurological, psychiatric, musculoskeletal and other diseases.

Demographic information

- Date of birth
- Sex

9.5.2.2.2 Vital Signs

Measurements of vital signs (spO₂, systolic and diastolic blood pressure, respiratory rate as well as pulse rate) and treatment parameters on normal ward, IMCU/ICU (Organ support, including resp. settings and FiO₂) will be performed at the time-points specified in Table 1. All measurements of vital signs must be recorded in the appropriate source documents.

9.5.2.2.3 Height and Weight

Measurements of height and weight will be performed according to the schedule in Table 1.

Height is measured in centimetres and weight is measured in kilograms. If feasible, measurements are to be taken in light clothing and socks (without shoes) with pockets emptied. The patient's height is recorded to the nearest 1 cm and weight is recorded to the nearest 1 kg.

9.5.2.2.4 Clinical Laboratory Evaluations

All laboratory assays will be performed according to the laboratory's normal procedures. Reference ranges will be supplied by the laboratory and used to assess the laboratory data for clinical significance and out-of-range pathological changes. The Investigator should assess out-of-range laboratory values for clinical significance, indicating if the value(s) is/are not clinically significant or clinically significant. Abnormal laboratory values that are unexpected or not explained by the patient's clinical condition may be, at the discretion of the Investigator or Sponsor, repeated until confirmed, explained, or resolved as soon as possible.

9.5.2.2.4.1 Pregnancy Test

Appropriately performed using blood test.

9.5.2.2.5 Concomitant Medication

Concomitant medication will be assessed at the time points described in Table 1.

9.5.3 Primary efficacy variable(s)

9.5.3.1 Outcome Measures

Patient-related parameters were defined as outcome measures obtained by the respective gold-standards.

9.5.3.1.1 Clinical Laboratory

All relevant clinical laboratory variables obtained during screening, final examination or the clinical trial periods will be reported in appropriate tables together with descriptive statistics in the CSR.

9.5.3.1.2 Vital Signs

Blood pressure and pulse rate descriptive statistics will be listed by sampling times (screening and follow-up) according to the data captured in the eCRF.

9.6 Data Quality Assurance

9.6.1 Documentation and Data Collection

The eCRF will be prepared to report at least all clinical data required by the protocol. Site staff will transfer the study data from the source documents into the eCRF. Site staff will check eCRF entries for completeness. Completed eCRF modules will be electronically signed by an Investigator in order to ensure data entry accuracy.

Research Coordinators will enter the study data in a structured Data Collection Form (e.g. REDCap online software (www.project-redcap.org)).

9.6.2 Data Quality Monitoring

Site staff will enter data electronically through the validated eCRF system. Quality control will include regular data verification and protocol compliance checks.

Data management will check predefined eCRF entries as defined in the data management plan (DMP), which will be locked after all queries and discrepancies that may occur during data entry are resolved.

Upon request safety reports and interim analysis (50 % of randomized patients) will be generated and provided to the respective members of the DSMB.

After database lock, the data in the study database will be exported and transferred electronically to the responsible biostatistician for statistical analysis. The datasets will be used to generate the patient listings, tabulations, and analyses for the CSR.

9.6.3 Archival of documents

The research team at each participating site will collect and record study data, as outlined in the data collection system (e.g. REDCap). On all study documents, specific patient data will be identified with unique study identifiers. Trial data will be stored in a secured hospital network drive. Once the trial recruitment period is complete, all study data will be securely stored. The Sponsor will maintain the trial documents and take measures to prevent accidental or premature destruction of these documents. All documents related to the study will be retained until at least 15 years after the end of the study.

9.7 Statistical Methods Planned in the Protocol and Determination of Sample Size

9.7.1 Statistical and Analytical Plan

A Statistical Analysis Plan (SAP) providing greater detail of data derivations and analyses to be performed will be completed prior to randomization of the first patient. The SAP will be reviewed and (if required) updated based on a blind review of the data prior to the analysis and will reflect the protocol and any amendments implemented at the time the SAP is updated.

9.7.1.1 Software to be Used

All statistical analyses will be carried out using SAS® language and procedures (SAS® 9.4 or higher version, SAS-Institute, Cary NC, USA), R (R 4.0.3 Development Core Team, Vienna, Austria).

<http://www.R-project.org>), Stata (Stata 16.0 or higher version, StataCorp., College Station, TX, USA), or SPSS (24.0 or higher version, IBM Corp., Armonk, NY, USA).

9.7.1.2 Eligibility for Statistical Evaluation

Eligibility of patients will be determined in a BDRM before statistical analysis will be performed.

9.7.1.2.1 Analysis Population

9.7.1.2.1.1 Full analysis set

The full analysis set (FAS) is as complete as possible and as close as possible to the intention-to-treat (ITT) ideal of including all randomised patients. Patients are analysed as belonging to their randomised arm, regardless of whether they received the intervention as planned, or whether other protocol deviations are known.

9.7.1.2.1.2 Per Population set

The per protocol set (PPS) comprises all patients of the FAS who had no relevant violations from the trial protocol. The blinded endpoint committee will define protocol violations that lead to exclusion from the per protocol population. Patients are analysed as belonging to their randomized arm.

9.7.1.2.1.3 Evaluated for safety set

The evaluated for safety set (EFS) comprises all patients of the FAS who received any intervention within the trial. The blinded endpoint committee will define assignment of individual patients to the safety population. Patients are analysed as belonging to their randomized arm.

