2 SYNOPSIS

Title of study	Awake PRO ne Positioning in PatientS with Acute Hypoxemic Respiratory Failure in Germany – A Randomized Controlled Study
Coordinating Principal Investigator	Acronym: PROSA [name]
Deputy-PI Study coordinator	[name], MBA
Deputy study coordinator	[name]
Trial manager	[name], PhD, MBA
Study centre	University Medical Center Hamburg-Eppendorf Department of Intensive Care Medicine [name], Germany
Clinical Trials-No.	N/A
Study Period	First patient in to last patient out (months): 18.0 Duration of the entire trial (months): 30.0 (6 months preparation, 18 months trial conduction, 6 months reporting) Recruitment period (months): 18 FPFV: Q2/2025 LPLV: Q4/2026
Phase of development	Phase 4
Medical condition	Acute Hypoxemic Respiratory Failure due to Pneumonia
Objective(s)	
 i. To evaluate if the application of standard awake prone positioning in spontaneous breathing patients (defined as patients without invasive mechanical ventilation or extracorporeal respiratory support) with acute hypoxic respiratory failure due to pneumonia at the intensive care unit (ICU) is superior to standard supine/semi-recumbent position in reduction of the rate of tracheal intubation and/or all-cause death within 28 days after randomization. ii. To assess safety and tolerability of awake prone positioning in patients with acute hypoxic respiratory failure due to pneumonia on the ICU.
Hypothesis	Prone positioning has shown beneficial effects in intubated patients with severe respiratory failure and positive effects in awake patients with COVID-19 pneumonia. Since the pandemic the rate of awake prone positioning has increased and became a standard medical therapy in ICUs worldwide. Conclusive evidence for patients with AHRF without COVID-19 is still missing. We hypothesis that awake prone position in patients with AHRF is beneficial in terms of reducing the rate of tracheal intubation and/or all-cause death.
Intervention	
Intervention:
 
 - Standard Awake Prone Positioning as defined by the study manual for a length of at least 72 hours

	
Control:
 
- Standard positioning (supine/semi-recumbent) (alone) of patients with acute hypoxemic respiratory failure according to the usual practice of each participating centre
 
Follow-up per patient:
 
Follow-up for all patients will be 28 days.

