
Statistical analysis
	
Efficacy: The objective of the trial is to prove superiority of the intervention arm versus the control arm. The primary analysis follows from the chosen adaptive design with one unblinded interim analysis after follow-up of 50% of the patients.
 
Description of the primary efficacy analysis and population: The primary analysis will follow the intention to treat (ITT) principle in the FAS (Full Analysis Set); that includes all randomised patients, as belonging to their randomisation arm, regardless of whether awake prone positioning could be applied as intended, or whether other protocol deviations are known. All details on the analyses will be detailed in a statistical analysis plan, which will be finalised prior to inclusion of the first patient. The adaptive analysis strategy for the primary endpoint follows the Inverse Normal method to independent test statistics derived from models on per-stage data. Each analysis (interim and final) will consist of a mixed logistic regression model comparing the primary outcome "tracheal intubation or all-cause death" between random groups with age and mode of respiratory support at inclusion as fixed effects and centre as random effect in order to map the stratified randomisation scheme. One-sided significance bounds for the two analyses are 0.0026 and 0.024. Overall, an alpha of 0.025 one-sided will be spent on the primary outcome.

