9.4 Interventional treatment

9.4.1 Study intervention

9.4.1.1 Clinical Intervention

The clinical intervention in the Intervention Group is Awake Prone Positioning, a standard therapy in intensive care units worldwide in ARDS care. The intervention should not be started later than 24 hours after randomization. An earlier start, as soon as possible, after randomization is strongly recommended. In patients in the intervention group standard Awake Prone Positioning for at least 10 hours/day for a length of 72 hours should be applied. To reach the targeted 10 hours / day (per 24 hours), it is strongly

recommended to use blocks of a longer time period (e.g. multiple 3-5 hours blocks) within the 24 h period to reach the anticipated APP goal. It is recommended that the APP therapy within the targeted intervention for 10 hours/day (per 24 h period) is not interrupted for more than 2 hours till reaching the goal of 10 hours / day (per 24 hours). It is further strongly recommended that one APP session should last at least 3 hours. Time in prone position may be prolonged if the patient is comfortable. A detailed instruction for APP can be found in the study manual.

Awake prone positioning will continue daily until the end of the 72 hours intervention period or one of the following stopping criteria is met before:

- 1) the patient is intubated
- 2) the patient is discharged from the ICU.

If patients have to be tracheal intubated and mechanically ventilated treatment should follow current ARDS guidelines according to the local protocol. This includes PP in patients with mild to severe ARDS if $\text{PaO}_2/\text{FiO}_2$ is below 150 mmHg.

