9.4.1.2 Control group

Patients randomized to the control arm will receive standard positioning at the discretion of the treating team but excluding APP. Control group patients will remain in their natural choice of position, which is anticipated to favour a supine, semi-recumbent position. The use of awake prone positioning as a so-called rescue intervention is discouraged in the control group and recorded as a protocol violation.

If patients have to be tracheal intubated and mechanically ventilated treatment should follow current ARDS guidelines. This includes PP in patients with mild to severe ARDS if $\text{PaO}_2/\text{FiO}_2$ is below 150 mmHg.

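### The safety set requires receipt of an intervention, which only the prone arm has to start; AE/SAE should be tabulated by arm in the full analysis set under a fixed rule

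*Protocol*

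**What the plan says.** Protocol section 9.7.1.2.1.3: "The evaluated for safety set (EFS) comprises all patients of the FAS who received any intervention within the trial". The same paragraph keeps patients in their randomised arm and has the blinded endpoint committee decide which individuals belong to the set. Section 9.7.1.2.2.1 places all safety analyses in this set and asks for AE and SAE rates by treatment group.

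The full analysis set (FAS), by contrast, keeps patients "regardless of whether they received the intervention as planned" (section 9.7.1.2.1.1). The synopsis gives the same rule as "regardless of whether awake prone positioning could be applied as intended".

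On what is received, section 9.4.1.1 states: "The clinical intervention in the Intervention Group is Awake Prone Positioning". On timing it adds: "The intervention should not be started later than 24 hours after randomization". For controls, section 9.4.1.2 states: "Patients randomized to the control arm will receive standard positioning at the discretion of the treating team but excluding APP", and then: "Control group patients will remain in their natural choice of position, which is anticipated to favour a supine, semi-recumbent position". The synopsis row on the intervention also describes the control, under its own subheading, as standard positioning "of patients with acute hypoxemic respiratory failure according to the usual practice of each participating centre".

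**The concern.** Restricting a safety set to treated patients works when both arms have something to start. Here one arm must begin a manoeuvre and the other carries on as before. A control patient meets a condition of having received assigned positioning at the moment of randomisation. An APP-arm patient meets it only once a prone session takes place, and may deteriorate, improve, refuse or be intubated before then. The condition can therefore remove patients from one arm for reasons related to outcome, while the table is still labelled as randomised.

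At stake is the by-arm AE/SAE table. Safety and tolerability are a stated objective (synopsis; section 8.1), so its population should be fixed and symmetric. Beyond the sentence quoted, the protocol gives the committee no criterion. Deciding who was proned also requires information that largely reveals the arm.

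**Working it through.** **Plan figure used.** The protocol gives no size for the safety set. The only plan figure needed is 171 per group (section 9.7.1.3). It reproduces: 0.50 versus 0.35, one-sided 0.025, 80% power and pooled variance give 169.31 per arm; times the two-look O'Brien-Fleming factor 1.0078 this is 170.63, rounded up to 171. The unpooled variance named in the protocol gives 166.57 × 1.0078 = 167.87, so 168. The difference does not matter here.

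**Step 1: what the condition does to each arm.**
- Literally APP. Controls are managed without APP, and rescue proning is discouraged and counted as a violation (section 9.4.1.2). If 0% to 5% of controls are proned (assumed), 171 × 0 to 171 × 0.05 gives 0 to about 9 controls in the set.
- Assigned positioning. Controls qualify at once. Exclusions fall essentially on APP-arm patients who never had a session.
- Any care within the trial. Both arms receive standard therapy (section 7.5), so the set is the FAS, apart from anyone in either arm lost before any care.

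**Step 2: size under assigned positioning.** Let p be the true event rate in both arms, q the never-proned share of the APP arm and r the event risk among those removed. The protocol gives none of these; all are assumptions.

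APP-arm rate in the safety set = (p − q·r)/(1 − q).
Artefact = that rate − p = q·(p − r)/(1 − q).
Example: q = 0.03, p = 0.50, r = 0.70 gives 0.03 × (−0.20)/0.97 = −0.62 points.

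Artefact in percentage points at p = 0.50 (negative makes APP look safer):

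| q | patients of 171 | r = 0.9 | r = 0.7 | r = 0.5 | r = 0.3 | r = 0.1 |
|---|---|---|---|---|---|---|
| 3% | 5.1 | −1.24 | −0.62 | 0 | +0.62 | +1.24 |
| 5% | 8.6 | −2.11 | −1.05 | 0 | +1.05 | +2.11 |
| 10% | 17.1 | −4.44 | −2.22 | 0 | +2.22 | +4.44 |

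At p = 0.30, with r from 0.9 to 0.1, the range is −1.86 to +0.62 for q = 3% and −3.16 to +1.05 for q = 5%.

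**Step 3: scale.** The 95% sampling margin on a difference with 171 per arm at 50% is 1.96 × √(2 × 0.5 × 0.5/171) = 0.106, or 10.6 points.

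**Step 4: direction.** The sign follows p − r. If the never-proned are mainly early deteriorations, r exceeds p and APP is flattered. If they are mainly refusers or early improvers, r is below p and APP looks worse. The protocol does not settle which.

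**The case against.** A reader might infer that the safety table will have no control group, because section 9.4.1.1 identifies the intervention with APP. The documents do not support that as the intended meaning. The safety-set paragraph assigns patients to their randomised arms, and section 9.7.1.2.2.1 wants rates by treatment group; both presuppose controls.

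A reader might also say that the protocol contradicts itself on the word. That is too strong. The synopsis row lists APP and control under separate subheadings, and the two versions of the FAS rule are compatible. The fault is that the condition does not say what qualifies a control.

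Nor can it be said that only APP-arm patients could ever be excluded. Patients may withdraw at any time (section 9.3.3.3), and deferred consent may later be refused (sections 5.3 and 9.5.2.1), in either arm. Hence the qualifier: essentially only.

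The strongest defence is that the harm is small. Section 9.3.2 excludes patients unlikely or unable to prone or comply, which should keep the never-proned share low. The table is descriptive, and a treated-patients safety set is common. All of this stands. The blinding difficulty is also not peculiar to this set, since the per-protocol set needs adherence information too.

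Deferring the matter to the SAP answers less. Operational detail may properly sit there, but the protocol itself fixes a rule that works differently in the two arms, and a SAP could only repeat it or depart from it.

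**Conclusion.** The point holds in a limited form and is worth correcting. The stated rule permits a post-randomisation exclusion that falls essentially on one arm, decided case by case without a criterion, in a table presented as randomised.

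The likely distortion is about 0.6 to 2 points if 3% to 5% of the APP arm are never proned, the true rate is 50% in both arms, and the event risk among those removed lies between 10% and 90% but differs from 50% by at least 20 points. It vanishes if that risk equals 50%. A never-proned share of 10% would be needed to reach about 4.4 points. Every input is assumed and the direction is unknown.

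A reader might go on to infer a material bias in favour of APP or a threat to the trial's main result. Neither follows: the illustrated shift at 3% to 5% is well inside the sampling margin, and the primary and secondary efficacy endpoints are analysed in the FAS (section 9.7.1.2.2.1).

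**What to change.** Amend sections 9.7.1.2.1.3 and 9.7.1.2.2.1 as follows:
- Tabulate AE and SAE by randomised arm in the FAS, counting events from randomisation in both arms.
- Report APP-specific events (intolerance, APP-related events) additionally and descriptively among patients with at least one prone session. This fits the synopsis, which already plans descriptive safety endpoints for the APP group.
- Let this fixed rule replace the committee's case-by-case assignment to the safety set.

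The cost is two or three sentences and no new data. The downside is slight dilution of APP-caused event rates in the by-arm table. If such events occur only in proned patients, an assumed 20% would appear as 0.20 × 0.97 = 19.4% with 3% never proned, 0.20 × 0.95 = 19.0% with 5%, and 0.20 × 0.90 = 18.0% with 10%. The ever-proned table shows the undiluted rate.

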9.7.1.2.2 Statistical Analyses

All statistical analyses will be carried out by the trial statistician. To preserve the blinding of the study's biometry team until the final analysis, the unblinded interim analysis will be conducted by a separate biometry team from the same institute. Baseline variables will be described by treatment group using appropriate summary statistics.

9.7.1.2.2.1 Primary, Secondary, and Safety Endpoints

The primary efficacy analysis will be performed according to the ITT principle and will therefore be based on the FAS. The adaptive analysis strategy for the primary endpoint follows the Inverse Normal method to independent test statistics derived from adjusted mixed logistic regression models on per-stage data obtained. This strategy allows the use of conventional stopping strategies of group sequential designs. Unbiased parameter estimates and confidence intervals can be obtained by using the theory of repeated confidence intervals. In detail, the null hypothesis will be tested at overall one-sided type-one error of 2.5% with stopping boundaries according to an O'Brien and Fleming α -spending function. To account for the adaptive design of the trial, the Inverse Normal method will be used with weights $w_1=w_2=\sqrt{0.5}$ at the interim and final analysis, respectively. The test on treatment difference at each stage k ($k=1,2$) will be based on a Wald test statistic originating from a mixed logistic regression model including the treatment group (intervention versus control alone), age and respiratory status at randomization fixed effects and centre as random effect to reflect the stratified randomization. To ensure that the stage-wise test statistics are independent, the data are divided into two subsets, a first-stage and a second-stage data set.

Interim analysis:

After follow-up of 50% of the planned patients, an interim analysis with the possibility to stop for efficacy or futility will be conducted. The treatment effect is tested using the Inverse Normal method applied to the Wald test statistic (originating from the adjusted mixed logistic regression model) at interim significance level which is determined by an O'Brien and Fleming type α -spending function. If the trial is continued to stage 2, the sample size re-calculation will be based on conditional power, with a target conditional power of 80%. After re-calculation, the sample size is adjusted with the originally calculated sample size and the maximum sample size of 342 as lower and 513 upper limit for the adjusted sample size.

Final analysis:

The second-stage data for the final analysis will be based on the Inverse Normal combination of the Wald statistics from the adjusted mixed logistic regression models of the first- and second-stage data

(with weights $w_1=w_2=\sqrt{0.5}$) at local significance level according to the α -spending function. Parameter estimates and confidence intervals are calculated based on the theory of repeated confidence intervals (RCI), where the midpoint of the two-sided RCI is used as point estimate.

Secondary endpoints: Secondary efficacy endpoints will be analysed in the FAS. Treatment effects will be calculated with two-sided 95% confidence intervals. P-values and confidence intervals derived from these analyses are of descriptive nature only. Secondary outcomes will be analysed depending on the scale type. Time-to-event outcomes will be analysed by Cox proportional hazard models including centre as frailty term. Dichotomous variables will be tested by mixed logistic regression with centre as random effect. Continuous variables will be analysed with linear mixed effects models that include the baseline determinations of the outcome and centre as random effect. Scale transformations will be considered based on the pooled data set. In further secondary analyses, the effect of the number of hours with awake prone positioning on the primary and secondary endpoints is evaluated for the intervention group.

Safety endpoints: Safety analyses will be performed in the EFS. Rates of adverse events and serious adverse events will be tabulated by treatment group, according to type of event and system organ class.

9.7.1.2.2.2 Dropouts

It should be emphasised that as little patients as possible should discontinue treatment (or change to the other treatment arm) and that all patients should be followed up and also documented after discontinuation of the treatment in order to record data required according to the intention-to-treat principle. All efforts will be made to avoid missing data and to collect outcome data for all patients randomized in the trial. In the primary analyses, a negligible number of drop-outs is expected. In case of substantial dropout multiple imputation will be applied in sensitivity analyses.

